Numerous studies have found NTX to be safe and rarely associated with toxicity or severe side effects. These side effects appear to be dose-related and are less likely to occur at the dose proposed in this study. The most frequently reported side effects are gastrointestinal in nature, including epigastric pain, nausea and vomiting. Other, less frequent side effects include nervousness, headaches, low energy, sweating, joint and muscle pain, blurred vision and insomnia. Hepatotoxicity can occur but typically at much higher doses (e.g., 200-300 mg daily) and resolves when NTX is discontinued. Additionally, case reports have reported elevated liver enzyme tests in patients who were taking non-steroidal anti-inflammatory drugs in combination with high-dose NTX. In this study, physicians will have the option to instruct patients to initiate NTX at a dose of 25mg of oral NTX for 4 days and then 50mg per day. NTX has been shown to have an effect on the embryo in the rat and the rabbit when given in doses approximately 140 times the human therapeutic dose. Thus, we will instruct Addiction Psychiatrists not provide NTX to pregnant or nursing women or those who do not agree to use a reliable form of birth control. Before FDA approval, extended release NTX was studied in more than 900 patients ¹¹⁰. Extended release NTX appears to be generally well tolerated, and adverse effects tend to be mild ^{110, 110}. Patients using extended release NTX do not develop tolerance for or dependence on the medication. The extended release formula has been shown to be safe, tolerable, and efficacious in the treatment of alcohol use disorders.¹¹⁰ In a large 6-month multi-site study in the treatment of alcohol dependence the most common adverse events (AEs) were nausea, headache, and fatigue. Nausea was mild or moderate in 95% of cases; however, the large majority of these cases occurred only during the first month of treatment. The most common injection site reaction was tenderness. A recent large study of extended release NTX found that mean liver enzymes did not change significantly over the course of treatment and there was no effect of medication on the proportion of patients in the different groups who had liver enzyme elevations higher than 3 times the upper limit of normal ¹¹⁰. In addition, it has been found to be safe for use in patients with mild to moderate liver impairment ¹¹⁰ with evidence of a 15% greater reduction in liver enzyme levels in the NTX group as compared with the placebo group ¹¹⁰.

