Disulfiram: Disulfiram can cause minor side effects that typically occur during the first 2 weeks of therapy and wane either spontaneously or after a decrease in dose. These include acneiform eruptions, headache, allergic dermatitis, impotence, mild drowsiness, metallic aftertaste and fatigue. Hepatic toxicity including hepatic failure have been reported.¹¹⁰ Severe hepatitis associated with disulfiram may develop even after many months of treatment. Hepatic toxicity has occurred in patients with or without a history of abnormal liver function. Other severe side effects of disulfiram include optic neuritis, neuropathy, and psychosis. Monitoring of liver function, to assess for hepatotoxicity, will be important, especially in HIV/HCV co-infected patients. There are recognized medication interactions between disulfiram and several medications commonly used in HIV+ patients including metronidazole, isoniazid, rifampin, warfarin, benzodiazepines, oral hypoglycemics, desipramine, elavil, dilantin, theophylline that can lead to medication discontinuation or changes in dose.¹¹⁰

Interaction of alcohol pharmacotherapies and alcohol: NTX has been shown to reduce the number of drinks consumed in the laboratory and in the clinic. No safety concerns have been identified in these studies when alcohol is consumed in combination with NTX. There is no evidence that individuals attempt to over-ride the effects of NTX by drinking more. NTX does not block the aversive effects of alcohol consumption which serve to limit drinking.

Acamprosate, like NTX, can be continued in patient who continue to consume alcohol. Disulfiram, which has been used clinically for more than 60 years, blocks the enzyme aldehyde dehydrogenase resulting in a rapid buildup of aldehyde. This disulfiram-alcohol reaction begins 10-30 minutes after the ingestion of alcohol. The severity of the disulfiram-alcohol reaction varies from moderate to severe and includes nausea, emesis, vertigo, syncope, arrhythmia, and seizure. For this reason, patients who are prescribed disulfiram are instructed to avoid any product containing alcohol, including mouthwash.

Counseling There are no significant adverse effects of participating in the counseling intervention portion of this study provided by the Social Worker or Addiction Psychiatrist. Participation is likely to be of benefit.

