Breathalyzer, blood/urine collections: Breathalyzer and blood and urine collections are performed primarily as safeguards and should add no risks other than those normally associated with these procedures.

Rating scales and questionnaires: Rating scales, structured interviews, and questionnaires are all non-invasive, and should also add no risks to subjects, as our past experience indicates.

Recorded sessions: Participants will be made aware during the informed consent process that sessions with the study Social Worker will be digitally recorded and that the nature of these sessions will involve participants speaking about information regarding their health status, alcohol use, HIV status, medical history, and participation in the study. However, participant names will never be recorded on the tapes and the tapes will be coded by participant number rather than name in order to protect participant confidentiality. Participants will be given the option to decline to be taped during the study.

Risks include inconvenience and concerns about confidentiality.

7. **Minimizing Risks:** Describe the manner in which the above-mentioned risks will be minimized.

Protection against risk:

As the safety of alcohol pharmacotherapy has not been established in pregnant and nursing women, they will be excluded from participation. Women of child-bearing capacity must agree to use a reliable form of birth control. Pregnant women will be referred for other alcohol treatment. Women who become pregnant during the study will be taken off study medications immediately.

NTX: Addiction Psychiatrists will be instructed to avoid prescribing NTX in patients with medical conditions that would contraindicate the use of NTX. We will instruct Addiction Psychiatrists to exclude individuals from receiving NTX if they have evidence of significant hepatocellular injury (AST, ALT > 5 times the upper limit of normal or a diagnosis of cirrhosis and Child-Pugh class greater than A or B). We will instruct Addiction Psychiatrist to monitor liver enzyme tests prior to, during, and at end of treatment and a subject whose AST or ALT rises to > 5 times the upper limit of normal will have laboratory tests repeated in one week. If liver enzymes are persistently elevated or if the individual is symptomatic, we will instruct Addiction Psychiatrists to consider discontinuing NTX and refer patients for a Hepatology evaluation.

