Acamprosate: We will instruct Addiction Psychiatrists to avoid prescribing acamprosate in patients with medical conditions that would contraindicate its use. Individuals should not receive acamprosate if they have evidence of renal insufficiency with a creatinine clearance of less than 30 mL/min. For those subjects with a creatinine clearance of 30-50 ml/min physicians can use a reduced dose of 333 mg per day.

Disulfiram: We will instruct Addiction Psychiatrists to avoid prescribing disulfiram in patients with medical conditions that would contraindicate its use. Individuals should not receive disulfiram if they have evidence of severe coronary artery disease or psychosis. There is no known evidence that suggests that patients with preexisting liver disease are more likely to experience severe hepatotoxicity from disulfiram yet caution should be exercised in those with hepatic decompensation. We will instruct Addiction Psychiatrists to monitor liver enzyme tests prior to, during, and at end of treatment and a subject whose AST or ALT rises to > 5 times the upper limit of normal will have laboratory tests repeated in one week. If liver enzymes are persistently elevated or if the individual is symptomatic, we will instruct Addiction Psychiatrists to consider discontinuing NTX and refer patients for a Hepatology evaluation.

Rating scales and questionnaires The major risk of the assessments is the potential loss of confidentiality which is discussed in the section related to confidentiality below. To minimize any discomfort associated with reporting on sensitive behaviors, participants will be informed that they may refuse to answer questions that they are not comfortable answering. Questions related to eligibility determination and monitoring of safety and treatment response are not optional. If a person declines to answer these questions, we will advise them that they will not be able to participate and we will make a referral to other treatment if they are interested.

Digitally recorded sessions: All appropriate actions will be taken by staff members in order to minimize the risks associated with loss of confidentiality. Audio files will be coded by number and will be erased 6 years after the completion of the study.

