Disulfiram: Disulfiram can cause minor side effects that typically occur during the first 2 weeks of therapy and wane either spontaneously or after a decrease in dose. These include acneiform eruptions, headache, allergic dermatitis, impotence, mild drowsiness, metallic aftertaste and fatigue. Hepatic toxicity including hepatic failure have been reported.⁷⁰ Severe hepatitis associated with disulfiram may develop even after many months of treatment. Hepatic toxicity has occurred in patients with or without a history of abnormal liver function. Other severe side effects of disulfiram include optic neuritis, neuropathy, and psychosis. Monitoring of liver function, to assess for hepatotoxicity, will be important, especially in HIV/HCV co-infected patients. There are recognized medication interactions between disulfiram and several medications commonly used in HIV+ patients including metronidazole, isoniazid, rifampin, warfarin, benzodiazepines, oral hypoglycemics, desipramine, elavil, dilantin, theophylline that can lead to medication discontinuation or changes in dose.⁷⁰

Interaction of alcohol pharmacotherapies and alcohol: NTX has been shown to reduce the number of drinks consumed in the laboratory and in the clinic. No safety concerns have been identified in these studies when alcohol is consumed in combination with NTX. There is no evidence that individuals attempt to over-ride the effects of NTX by drinking more. NTX does not block the aversive effects of alcohol consumption which serve to limit drinking.

Acamprosate, like NTX, can be continued in patient who continue to consume alcohol. Disulfiram, which has been used clinically for more than 60 years, blocks the enzyme aldehyde dehydrogenase resulting in a rapid build-up of aldehyde. This disulfiram-alcohol reaction begins 10-30 minutes after the ingestion of alcohol. The severity of the disulfiram-alcohol reaction varies from moderate to severe and includes nausea, emesis, vertigo, syncope, arrhythmia, and seizure. For this reason, patients who are prescribed disulfiram are instructed to avoid any product containing alcohol, including mouthwash.

3. Source: a) Identify the source of the drug or biologic to be used.

Alcohol pharmacotherapies will be provided through routine clinical care by the pharmacies at the 7 Medical Centers.

b) Is the drug provided free of charge to subjects? Yes No
If yes, by whom?

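### The liver-enzyme rule for patients on disulfiram tells prescribers to consider stopping naltrexone instead

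*Combined protocol and SAP*

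**What the plan says.** Patients in the CM plus stepped care arm who are stepped up at 3 months see an Addiction Psychiatrist, who may prescribe disulfiram, oral or injectable naltrexone, or acamprosate. Section V, item 7 has a separate risk-minimisation paragraph for NTX, acamprosate and disulfiram.

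The Disulfiram paragraph names severe coronary artery disease and psychosis as reasons not to prescribe, and asks for caution in hepatic decompensation. It then requires liver-enzyme tests before, during and at the end of treatment. A patient whose AST or ALT exceeds 5 times the upper limit of normal "will have laboratory tests repeated in one week". If the elevation persists or the patient has symptoms, "we will instruct Addiction Psychiatrists to consider discontinuing NTX and refer patients for a Hepatology evaluation".

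On the liver risk of disulfiram, Section V, item 6 (Risks) states: "Hepatic toxicity including hepatic failure have been reported". Both that item and Section VI.A, item 2 (Background Information) add: "Severe hepatitis associated with disulfiram may develop even after many months of treatment".

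**The concern.** The paragraph is about disulfiram from its label through its contraindications and its liver monitoring. Its last step should therefore say what to do with disulfiram. It names naltrexone. Item 6 defines NTX as naltrexone, and Section VI.A, item 1 lists the two as separate medications. The paragraph does not mention combined use, so it cannot be read as a deliberate instruction to withdraw naltrexone from a patient taking both.

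Read literally, a patient on disulfiram with persistent enzyme elevation is referred to Hepatology, and the prescriber is prompted to consider stopping a drug the patient may not be taking. The prompt to consider stopping the suspect drug is missing. That matters more for disulfiram than for naltrexone on the protocol's own account:

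- Naltrexone hepatotoxicity is described as typical of much higher doses, and it "resolves when NTX is discontinued". Disulfiram is described as capable of causing hepatic failure, in patients with or without earlier liver abnormality.
- The NTX paragraph bars prescribing when AST or ALT exceeds 5 times the upper limit, or in cirrhosis worse than Child-Pugh class B. The Disulfiram paragraph has no such bar, only the advice on caution, so more rests on the on-treatment rule.
- Patients can qualify for the trial through detectable HCV or a FIB-4 above 1.45, so some will enter with existing liver disease.

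**Working it through.** No arithmetic applies. The check has two parts: compare the two paragraphs, then look for any text elsewhere that supplies the missing instruction.

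**Step 1. The two paragraphs in Section V, item 7.**

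| Element | NTX paragraph | Disulfiram paragraph |
|---|---|---|
| Drug covered | Naltrexone | Disulfiram |
| Liver bar to starting | AST/ALT above 5 times the upper limit, or Child-Pugh worse than B | None; caution in hepatic decompensation |
| Monitoring | Before, during and at end of treatment | Same |
| Trigger | AST or ALT above 5 times the upper limit; repeat in one week | Same |
| Drug to consider stopping | NTX | NTX |
| Referral | Hepatology | Same |

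The closing sentence, which sets the condition and then says to "consider discontinuing NTX and refer patients for a Hepatology evaluation", has 28 words and is the same word for word in both paragraphs. The monitoring sentence before it differs by one letter (Psychiatrist in the NTX paragraph, Psychiatrists in the Disulfiram paragraph). The drug name is the one thing that had to change when the text was reused, and it did not.

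**Step 2. Is there a disulfiram stopping instruction anywhere else?** Words beginning *discontinu-* occur six times in the document:

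| Place | Subject | Instruction to the prescriber? |
|---|---|---|
| Section V, item 6, naltrexone | Naltrexone liver toxicity resolves on stopping | No |
| Section V, item 6, disulfiram | Interactions with other drugs "that can lead to medication discontinuation or changes in dose" | No |
| Section V, item 7, NTX | Liver enzymes | Yes, names NTX |
| Section V, item 7, Disulfiram | Liver enzymes | Yes, names NTX |
| Section VI.A, item 2, naltrexone | Naltrexone liver toxicity resolves on stopping | No |
| Section VI.A, item 2, disulfiram | Interactions with other drugs | No |

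Two of the six are instructions, and both name NTX. The other four are background statements of risk, where no instruction would be expected. They are listed only to show that none of them fills the gap.

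**Step 3. Other wording for stopping a drug.** The only other instruction of this kind is the pregnancy rule in Section V, item 7: "Women who become pregnant during the study will be taken off study medications immediately". It has nothing to do with liver injury. The two descriptions of disulfiram risk (Section V, item 6 and Section VI.A, item 2) call liver monitoring important but give no action on the drug.

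**Result.** The Disulfiram paragraph names the wrong drug, and the protocol contains no instruction to consider stopping disulfiram for liver injury.

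**The case against.** The error itself is hard to dispute; the case on the other side is that it hardly matters.

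- The wording is advisory, and Section V, item 3 (Addiction Physician Management) leaves drug, dose and duration to the prescriber.
- For a patient on disulfiram alone there is no naltrexone to stop, so the sentence causes no wrong act. What is lost is a prompt. Monitoring, the one-week repeat and the Hepatology referral remain.
- The prescribers are certified Addiction Psychiatrists, trained with federal guidance on alcohol pharmacotherapy and supervised monthly. They would probably recognise the slip from its context.
- Exposure is narrow. Only CM-arm patients with a PEth above 8 ng/ml at 3 months reach this care, naltrexone is the drug that prescribers are encouraged to consider, and disulfiram is one of four options.
- The PI reviews safety at least quarterly and after any serious adverse event.
- The documents do not show the encounter forms or training material actually given to prescribers, so the slip may never have reached the sites.

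All of this stands, and it limits the likely harm. It also makes clear that this is a drafting error in safety text, with no methodological choice behind it. It does not supply the missing instruction. Each of these safeguards depends on someone noticing the mistake or acting without the rule that the protocol meant to give.

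**Conclusion.** The concern holds. The final sentence of the Disulfiram paragraph names naltrexone where it must mean disulfiram, and no other text corrects it.

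In the text, the error is one wrong word in one of the two liver-related stopping instructions. Its effect on patients cannot be quantified: the documents give neither how many patients will receive disulfiram nor how many of those will have persistent elevation or symptoms, and the number could be zero. Sample size, power and analysis are not affected.

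The conclusion rests on one inference: that the paragraph is meant to govern disulfiram throughout. Its label, its contraindications and its match with the NTX paragraph all support that. It should be fixed because the text is a safety rule that is wrong as written; no prediction of injury is needed.

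**What to change.** In the last sentence of the Disulfiram paragraph of Section V, item 7, replace NTX with disulfiram, so that the action is to consider stopping disulfiram and to refer to Hepatology. Leave the NTX paragraph unchanged, since the sentence is correct there. Check the structured encounter forms and training material for the same slip, and send the Addiction Psychiatrists at the sites a short notice of the correction.

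The cost is one word and one notice. Schedule, data collection, sample size and analysis stay as they are.

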- b. Medical condition impacted by alcohol** as evidenced by one of the following: 1) detectable HIV viral load (>200 copies/ml),⁵⁰ 2) smoked at least 100 cigarettes in their lifetime and who now report smoking cigarettes every day or some days and have a positive exhaled CO test or urine cotinine test, 3) detectable HCV virus, 4) liver fibrosis with a FIB-4 >1.45,⁵¹ 5) Patient Health Questionnaire (PHQ-9, validated measure for depression) score greater than 9,⁵² or 6) current (at least 30 day supply in the past 60 days) prescription for a psychoactive medication that interacts with alcohol-including benzodiazepines, opioids, antipsychotics, antidepressants, sleeping medications and muscle relaxants.²¹
- c. Alcohol Use Disorder** – Meet DSM-5 criteria for alcohol use disorder, not in remission

Exclusion criteria: No subject may:

1. Be acutely suicidal, or with a psychiatric condition that affects his/her ability to provide informed consent or participate in counseling interventions (e.g. psychotic, dementia, delusional).
2. Be currently enrolled in formal treatment for alcohol (excluding mutual-help, e.g. Alcoholics Anonymous)
3. Have medical conditions that would preclude completing or be of harm during the course of the study.
4. Be a pregnant or nursing woman or women who do not agree to use a reliable form of birth control.
5. Have a current diagnosis of or be in remission for a gambling disorder given the gaming nature of CM based on >4 positive criteria on the National Opinion Research Center DSM Screen for Gambling Problems (NODS).

5. How will **eligibility** be determined, and by whom?

Participants will be recruited from their clinical sites of HIV care through screening and proactive recruitment. If they are interested, participants will meet with a research assistant who will describe the study in more detail, determine interest in participating, and assess potential eligibility. For potentially eligible patients, the research assistant will obtain written informed consent for screening. All participants' data will be evaluated by the research assistant and the site PI to verify eligibility. Individuals who do not meet eligibility criteria or who decline to take part in the study will be referred to appropriate treatment services. Once the subject has signed the consent, they may withdraw consent at any time.

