General considerations: This is a randomized, controlled, parallel group trial to evaluate the effectiveness of CM plus stepped care compared to TAU to reduce unhealthy alcohol use in HIV-infected individuals. Data analysis will be conducted by [name] and YCAS. The 6-month follow-up was chosen as the primary endpoint as we expect the most robust differences at this time and there is uncertainty in the shape of the treatment response over time. Average intervention group differences across all time points and slopes of change will be compared between groups in supportive secondary analysis. A type I error of 5% (two-sided) will be used to test for significance and analyses will be performed using SAS v9.2 (SAS Institute, Cary, NC).

Adequacy of sample size

The primary aim of the study is to determine whether CM plus stepped care will lead to a greater proportion of patients with PEth documented abstinence when compared to TAU. The primary outcome will be proportion of patients with self reported abstinence on Timeline Follow Back at 6 months, with PEth < 8 ng/ml at 6 months as a secondary outcome (Aim 1). Data from the TAU group in the **STEP** Trials, when restricted to those with a PEth > 20 ng/ml at baseline, reveals 11% spontaneous abstinence as assessed using PEth < 8 ng/ml at 6 months. We believe this provides a good estimate of the anticipated abstinence rate with TAU in the proposed trial. To detect a 15% difference (proportion demonstrating abstinence in CM plus stepped care of 26%) with 80% power at a two-sided 0.05 significance level, a sample size of 139 per group is required. Thus, we will enroll and randomize 348 patients to account for 20% dropout. Based on alcohol consumption in the TAU arms of the **STEP** Trials, and a standard deviation of 11.5, we will have 80% power to detect a difference of 3.9 in average drinks per week over the last 30 days, at 6 months. Data from the TAU group in the **STEP** Trials reveals that 29% of patients

experienced a 5-point decrease in the VACS Index at 6 months. With the proposed sample size, we will have 90% power, at a two-sided 0.05 significance level, to detect a 20% difference in this (Aim 2) outcome (proportion of patients who achieve a 5-point decrease in the VACS Index in CM plus stepped care of 49%). In our prior trials, including the **STEP** Trials, we have obtained completed 6-month assessments in 74-95% of enrolled subjects.^{60,61}

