A likelihood-based ignorable analysis using a generalized linear mixed model (GLMM) will be used to compare abstinence between groups.^{111,112} The primary advantage of the mixed model when compared to commonly used methods such as complete case analysis and single imputation (e.g. last observation carried forward) is its flexibility in handling missing data. This analysis makes use of all available outcome data at each timepoint and assumes that missing data occurs at random (i.e. not informative).¹¹³ The inclusion of 3, 6, 9 and 12 month outcome data in the model will assist in meeting this assumption. More specifically the mixed models will include fixed effects for intervention (CM plus stepped care vs. TAU), time (3, 6, 9, 12 months), and the interaction of intervention with time. Additional fixed effects will be included for baseline covariates: PEth, stratification group (at-risk drinking, medical condition impacted by alcohol, AUD), number of drinks per week, gender, VACS index and study site. Given the heterogeneity in the patient groups, the interaction between intervention and stratification group will be evaluated and included in the primary analysis at the p<0.10 significance level. Linear contrasts will be used to estimate intervention group differences and 95% confidence intervals at the primary 6-month outcome assessment. Similar contrasts will be performed at the other secondary follow-up times and supportive analyses examining the average and slope of change in abstinence rates across post-randomization time will be performed. Subgroup analyses will be performed to evaluate moderation of the intervention response by stratification group and study site. We will also use linear mixed effect models to compare continuous PEth and alcohol consumption using data from the TLFB.

Analysis for Aim 2: The primary objective of Aim 2 is to determine if HIV biomarkers (VACS index) differ between subjects receiving CM plus stepped care compared to those receiving TAU. The primary response will be defined as a 5-point improvement from baseline on the VACS index. As in Aim 1, a GLMM will be used to compare this response. We will use a repeated measures mixed model analysis with continuous VACS index as the outcome. As in Aim 1, we will perform subgroup analyses to evaluate moderators.

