Analysis for Exploratory Aims: For aim 3, we will evaluate the impact of the intervention in those with medical conditions on condition-specific outcomes such as HIV viral load, eCO or urine cotinine (for smoking cessation), FIB-4, detectable HCV virus, depressive symptoms and use of psychoactive medications that interact with alcohol. These analyses will focus on estimation rather than hypothesis testing and will be performed only in those identified with the specific medical condition at baseline. GLMMs will be used to describe these outcomes by treatment group and time. Treatment differences for continuous outcomes, odds ratios for dichotomous outcomes and rate ratios for count outcomes along with 95% CIs will be estimated.

Plan for Missing Data: Several strategies will be imposed to accommodate the likelihood of missing data. Prevention is the most effective manner to control bias and loss of power from missing data.¹¹⁴ In our prior alcohol trials we have obtained 6 month assessments in 95% and 88% of subjects.^{60,61} We will follow the intent to treat principle, requiring follow-up of all subjects randomized regardless of the treatment received.¹¹⁵ Telephone and text visit reminders will be sent to participants prior specified collection times. Timely data entry combined with weekly missing data reports will trigger protocols for tracking and obtaining missing data items. Despite these efforts it is reasonable to assume missing data will occur. Our primary analysis is valid under the assumption that missing data is missing at random (MAR).¹¹¹ We will evaluate the plausibility of this assumption by determining the extent of missing data and use logistic regression to identify factors associated with dropout. While we do not expect differential dropout rates between groups or high loss to follow-up, we will perform sensitivity analysis using pattern-mixture and selection models under missing not at random (MNAR) assumptions to examine the robustness of conclusions of the primary analysis to missing data.

Timeline and Milestones

SECTION VI: RESEARCH INVOLVING DRUGS, BIOLOGICS, RADIOTRACERS, PLACEBOS AND DEVICES

If this section (or one of its parts, A or B) is not applicable, state N/A and delete the rest of the section.

A. DRUGS, BIOLOGICS and RADIOTRACERS

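### The rule that declining a treatment-response question bars participation is not limited to the time before randomization, and conflicts with following everyone randomized

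*Combined protocol and SAP*

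**What the plan says.** Section V, item 7 (Minimizing Risks), in the paragraph on rating scales and questionnaires, starts with a general permission: "participants will be informed that they may refuse to answer questions that they are not comfortable answering". It then makes an exception: "Questions related to eligibility determination and monitoring of safety and treatment response are not optional". One consequence is given for the whole exception: "If a person declines to answer these questions, we will advise them that they will not be able to participate". A referral to other treatment is offered to anyone interested.

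Section V, item 9, under Plan for Missing Data, adopts intention to treat, "requiring follow-up of all subjects randomized regardless of the treatment received".

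Under Adequacy of sample size in the same item: "The primary outcome will be proportion of patients with self reported abstinence on Timeline Follow Back at 6 months". PEth-documented abstinence is now secondary. Under Analysis for Aim 1, the generalized linear mixed model is described as follows: "This analysis makes use of all available outcome data at each timepoint and assumes that missing data occurs at random".

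The schedule of assessments in the Research Plan places the TLFB, PEth and the VACS Index laboratory tests at baseline, weeks 12 and 24, and months 9 and 12.

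**The concern.** The exception names three kinds of question. Eligibility questions precede randomization. Questions that monitor safety and treatment response are, by their nature, also asked afterwards. The consequence attaches to all three without distinction, and no passage in the protocol confines it to screening.

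The primary outcome is now a self-report questionnaire, so the item a participant declines may be the primary outcome instrument itself. A site applying the sentence literally could turn one declined questionnaire into loss of everything that follows. That includes PEth, the objective secondary outcome and the best available evidence on what an unanswered TLFB might have shown. In the CM plus stepped care arm, the 3-month PEth also determines progression to Step 2.

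It is reasonable, though not shown in the documents, to expect people who are still drinking to be more willing to skip drinking questions. Only one arm is rewarded for abstinence. Loss triggered by such refusals could therefore depend on the outcome and differ between arms, which is what the missing-at-random assumption excludes.

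**Working it through.** No figure in the plan bears directly on this rule, so the check is mainly a reading of the text.

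**1. Does the rule reach randomized participants?** Eligibility is listed separately from monitoring of safety and treatment response. If the sentence covered screening only, the second and third categories would have nothing to act on, because there is no treatment to respond to. The paragraph concerns the study assessments in general, and the TLFB is scheduled at four visits after baseline. As worded, the rule reaches those visits.

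**2. Does it conflict with the follow-up rule?** The Plan for Missing Data covers all subjects randomized and makes no exception for a declined item. Its qualifier concerns treatment received, so it does not address item refusal expressly. A participant told they cannot continue is nevertheless a randomized subject who is not followed. The only other exit described, under item 5 (eligibility), is withdrawal of consent, which is the participant's own choice.

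**3. What would the rule cost beyond the refusal itself?** Counting from the assessment schedule (weeks 12 and 24, months 9 and 12):

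| TLFB declined at | Missing with or without the rule | Further TLFB assessments lost if participation ends | Visits with PEth and VACS labs lost |
|---|---|---|---|
| Week 12 | Week-12 TLFB | 3 (week 24, months 9 and 12) | up to 4 |
| Week 24 | Week-24 TLFB (primary) | 2 (months 9 and 12) | up to 3 |
| Month 9 | Month-9 TLFB | 1 (month 12) | up to 2 |
| Month 12 | Month-12 TLFB | 0 | up to 1 |

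The last column says *up to* because blood may already have been drawn at the visit where the question is declined. Under the pandemic arrangements in Follow-up assessments, the interview is done remotely and the laboratory and PEth part follows when a clinic visit is possible. In that format the refusal comes first.

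The rule removes a primary outcome value only from someone who declines at week 12 but would have answered at week 24. For someone who declines at week 24, the primary value is missing either way.

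**4. What does the model do with such a person?** The TLFB abstinence model uses outcomes at 3, 6, 9 and 12 months, with baseline values as covariates. Someone who declines at 3 months and stays in can contribute three outcomes. Someone whose participation ends there contributes none, and so adds nothing to the likelihood.

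**5. Is power the issue?** The plan allows for 20% dropout: 139 / 0.80 = 173.75, rounded up to 174 per group, or 348 in total. With 139 analysed per group, the pooled two-proportion test of 11% against 26% has 90.1% power. (The plan states 80%; that mismatch is a separate matter.) If refusals added an assumed 10 points to dropout, 174 × 0.70 = 121.8 per group would remain, with 85.9% power. These are PEth-based rates and serve only as context. They indicate that lost numbers are not the main worry; selective loss is.

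**The case against.** The strongest reply is that the sentence is an entry condition. It speaks of a person who cannot take part and offers a referral, much like item 5 on eligibility: "Individuals who do not meet eligibility criteria or who decline to take part in the study will be referred to appropriate treatment services". It does not mention withdrawal, stopping follow-up or excluding data. Where the same section means people already enrolled, as with pregnancy arising during the study, it says so. The Plan for Missing Data also expects item-level gaps, since weekly reports prompt staff to pursue missing items. The consent form is not in the reviewed text and may say more.

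This has weight. A reader might infer that the protocol orders the removal of randomized participants who decline a question. The documents do not say that, and site practice cannot be known from them. But the entry reading leaves the treatment-response category without a function. Even as an advance warning at consent, it leaves unsaid what happens when a randomized participant later declines.

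Two further points stand. First, the harm has limits. Pharmacy, diagnosis, utilization and laboratory data at VA sites come from the electronic record through the informatics core, and nothing says that extraction stops, so some laboratory values from routine care could survive. The plan also includes a regression of factors associated with dropout, and pattern-mixture and selection models for data not missing at random. These test robustness but do not recover PEth or TLFB data never collected.

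Second, a reader might try to size the bias by deleting some share of non-abstinent participants from one arm and recomputing the planned 26% versus 11%. That would not measure this rule. A declined 6-month TLFB is missing with or without it, no refusal rate is documented, and both planning rates rest on PEth while the primary outcome is self-report.

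**Conclusion.** The concern holds as an unreconciled conflict in the text. The participation rule extends, as written, to treatment-response and safety questions asked after randomization, and so conflicts with following all subjects randomized. What can be counted is the data exposed per participant if a site applied the rule at 3 months: three later TLFB assessments, one of them the primary outcome, and PEth and VACS laboratory tests at up to four visits. This rests on the literal reading and on participation ending at that visit.

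How many participants would be affected, and the size or direction of any bias in the treatment comparison, cannot be derived from the documents. The point should be corrected because it concerns a stated rule, touches the primary outcome instrument and is cheap to settle. It is not evidence that the trial has lost, or would lose, participants this way.

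**What to change.** In the rating scales and questionnaires paragraph, limit the participation consequence to eligibility questions asked before randomization. Add that after randomization a declined outcome question is recorded as missing for that item and visit only. The participant stays in the assigned arm for analysis. The remaining assessments at that visit, including PEth and laboratory tests, and all later scheduled visits continue unless the participant withdraws consent.

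The sponsor should separately reconcile how declined safety questions are handled with the Plan for Missing Data, keeping research follow-up distinct from any decision about study treatment. That clinical decision is outside this review.

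The cost is one paragraph of protocol amendment and matching consent wording, with no extra visits or staff. The small downside is some item-level missing data among participants who stay in, which the planned missing-data analyses can take up.
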